#### Dose Modification Guidelines

NCI Toxicity-Grade	Event	Action
	Hb $\geq 12$ gm/dL (not associated with RBC transfusion)	Discontinue *
$\geq$ Grade 3	Any adverse event	Dose delay **

\* Subject will discontinue the study drug.

\*\* Delay dose of TFP for up to 7 days or until AE severity improves to  $\leq$  Grade 1 or to Baseline status.

## 4 Study Objectives

### Primary Objective

- To evaluate the safety profile of a 21-day course of TFP at doses up to 10 mg/day in RBC transfusion-dependent adults with DBA

## 5 Resources Available to Conduct the Human Research

[name] is the PI and sponsor of this study and the Director of the Diamond Blackfan Anemia Registry (DBAR) of North America. The DBAR is housed at the Feinstein Institute for Medical Research. There are over 750 subjects with Diamond Blackfan anemia enrolled in the DBAR. Because of this, the investigator has access to the specific subject population required for this study. Subjects/parents of subjects and their physicians contact the DBAR periodically to inquire about available studies. Also, the DBA Foundation (DBAF), the family support group, has access to most of the DBA families. The DBAF is highly supportive of the research and they also encourage the families to contact the DBAR for any available studies. We have prepared an announcement to inform the subjects of the study as we have for other studies in the past. This has worked well previously, and we do not expect having any issues in recruiting subjects.

With regards to the trial logistics, the protocol is reviewed at the site initiation visit with all study personnel, along with the trial-related duties and functions.

## 6 Study Design

### 6.1 General Design

This study is a multi-center, Phase I/II, dose escalation, open-label study to determine the safety of TFP in adult subjects with DBA and RBC-transfusion-dependence. A 3+3 dose escalation regimen will be used. The maximum time on study drug will be 21 days with a 1 week post-treatment follow-up period. It is expected that up to 24 subjects can be recruited and complete the study within 12-18 months. The dose escalation study design is shown in Figure 1:

- If 2 or more of the 6 subjects in Cohort B demonstrate toxicity  $\geq$  Grade 3, the study will be stopped, and 1 mg/day will be declared the MTD.
  - If  $< 2$  of the 6 subjects in Cohort B demonstrate toxicity  $\geq$  Grade 3 within 21 days of starting therapy, Cohort C will start.
3. Cohort C: Three subjects will receive TFP 5 mg PO daily.
- If there is no toxicity  $\geq$  Grade 3 at the end of the 21 days, Cohort D will start.
  - If 1/3 subjects in Cohort C demonstrates toxicity  $\geq$  Grade 3, an additional 3 subjects will be enrolled in Cohort C:
    - If 2 or more of the 6 subjects in Cohort C demonstrate toxicity  $\geq$  Grade 3, the study will be stopped, and 2 mg/day will be declared the MTD.
    - If  $< 2$  of the 6 subjects in Cohort C demonstrate toxicity  $\geq$  Grade 3 within 21 days of starting therapy, cohort D will start.
4. Cohort D: Three subjects will receive TFP 10 mg PO daily.
- If 0/3 subjects in Cohort D demonstrates toxicity  $\geq$  Grade 3, the study will be stopped, and 10 mg/day will be declared the MTD.
  - If 1/3 subjects in Cohort D demonstrates toxicity  $\geq$  Grade 3, an additional 3 subjects will be enrolled in Cohort D.
  - If 2 or more of the 6 subjects in Cohort D demonstrate toxicity  $\geq$  Grade 3, the study will be stopped, and 5 mg/day will be declared the MTD.
  - If  $< 2$  of the 6 subjects in Cohort D demonstrate toxicity  $\geq$  Grade 3 within 21 days of starting therapy, 10mg/day will be declared the MTD.

Each subject will undergo safety assessments as per the required schedule while on the study drug. All dosed subjects will be followed for an additional 1 week after discontinuing study drug (post-study safety follow-up). There will be no more than 6 subjects enrolled at any particular time.

Treatment will be discontinued for any subject if their Hb is > 12 gm/dL, not associated with RBC transfusions.

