This class of drugs has not been tested specifically in subjects with DBA prior to this study. To mitigate the potential risks of administering TFP to this new population, we will (1) start dosing at dose levels well below those prescribed for psychosis over the past several decades, (2) dose escalate to a maximum of 10 mg daily (the lowest dose typically prescribed for psychosis), and (3) perform weekly safety monitoring. Given the positive signal in DBA animal models and the 60-year clinical experience with higher doses of TFP, this drug warrants a trial in humans to assess tolerability in DBA. If tolerated, this trial will support either a PoC trial of low-dose TFP in DBA, or the advancement of a chemically modified TFP-like drug (to alleviate the neurologic toxicity) for the treatment of DBA.

This is a dose escalation safety and tolerability study to evaluate the presence of TFP-related adverse events in DBA subjects, and to determine the maximum tolerated dose (MTD) of TFP in DBA. The dose escalation strategy is described in [Section 3.5 Dose Rationale and Risk/Benefits](#).

Some first-in-human (FIH) trials may implement an enrollment restriction rule such that two subjects are dosed in a given cohort, and a third subject is not dosed until both of the first two subjects have demonstrated tolerability. For this trial, we have elected not to use such an enrollment restriction design for the following reasons:

- a. This is not a FIH trial: TFP has been in wide clinical use for 60 years.
- b. Our dose levels (1 mg daily, up to max 10 mg daily) are all well within and below the safe range of clinical use. Doses in the 2-6 mg daily range have been shown to have a side effect profile similar to placebo in patients with anxiety ([Mendels, 1986](#)). A randomized clinical trial comparing TFP 15 mg/day vs. placebo in schizophrenic subjects revealed no difference in the rates of severe adverse effects, Parkinsonism or dystonia compared to placebo (Koch, 2014). Doses for psychosis range from 10 mg daily up to 40-50 mg daily, whereas we will dose at 1, 2, 5, and 10 mg daily only.

- c. We will monitor for safety, specifically for any hematologic toxicity and for extrapyramidal/central nervous system (CNS) effects. Dose escalation criteria and actions, as well as subject and cohort stopping rules are detailed in [Section 6 Study Design](#).

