## **15.4 Stopping Rules**

The stopping rules are as follows:

Scenario 1: The occurrence of extrapyramidal symptoms, symptoms suggestive of tardive dyskinesia (including vermicular movements of the tongue), neuroleptic malignant syndrome or any SAE or treatment-emergent AE  $\geq$  Grade 3 felt to be causally related to TFP in a single subject:

- Rule: Treatment will be immediately stopped in that subject and the subject will be discontinued from the study.

Scenario 2: The occurrence of the extrapyramidal symptoms, symptoms suggestive of tardive dyskinesia (including vermicular movements of the tongue), neuroleptic malignant syndrome or the same SAE or treatment-emergent AE  $\geq$  Grade 3 felt to be causally related to TFP in more than 1 subject:

- Rules:
  - a. Treatment will be immediately stopped in those subjects and those subjects will be discontinued from the study.
  - b. If the 2 or more subjects are in Cohort A, the trial will be stopped; no MTD will be declared.
  - c. If the 2 or more subjects are in Cohort B, the study will be stopped, and 1 mg/day will be declared the MTD.

- d. If the 2 or more subjects are in Cohort C, the study will be stopped, and 2 mg/day will be declared the MTD.
- e. If the 2 or more subjects are in Cohort D, the study will be stopped, and 5 mg/day will be declared the MTD.

Scenario 3: Hemoglobin > 12 mg/dL in a subject sustained for more than 7 days (not associated with RBC transfusion)

- Rule: The subject will be considered a complete responder, treatment will be discontinued, and the duration of the effect will be monitored until day 29 after start of treatment.

In addition to the stopping rules, a subject may be discontinued by the investigator at any time for failure to comply with protocol requirements, in the event that the investigator feels that continuation in the study poses a risk to the health of the subject, or if the subject withdraws consent.

The reason for treatment discontinuation must be documented in the subject chart / source records.

The trial will be stopped, as noted above, if more than one subject experiences the occurrence of the extrapyramidal symptoms, symptoms suggestive of tardive dyskinesia, neuroleptic malignant syndrome, the same SAE or treatment-emergent AE  $\geq$  Grade 3 felt to be causally related to TFP at the lowest dose level.

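### Sections 6.1 and 15.4 can name different MTDs from the same cohort when neurologic events stay below Grade 3, and the available text does not rank them

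*Combined protocol and SAP*

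**What the plan says.** **Section 6.1 General Design.** The readable part covers the end of Cohort B and all of Cohorts C and D. It counts subjects with toxicity of Grade 3 or higher and mentions no other kind of safety event.

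- Cohort B, fewer than 2 of 6 subjects at or above "Grade 3 within 21 days of starting therapy, Cohort C will start".
- Cohort C, no toxicity at or above "Grade 3 at the end of the 21 days, Cohort D will start".
- Cohort D, 0/3 subjects at or above "Grade 3, the study will be stopped, and 10 mg/day will be declared the MTD". Fewer than 2 of 6 in an expanded Cohort D also gives 10 mg.

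**Section 15.4 Stopping Rules.** A second set of rules stops the study and names the MTD. The trigger opens: "Scenario 2: The occurrence of the extrapyramidal symptoms, symptoms suggestive of tardive dyskinesia". It continues with NMS, and then with the same SAE or treatment-emergent AE of Grade 3 or higher judged related to TFP, in more than one subject. Rules b to e give the result by cohort:

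- Cohort A: no MTD.
- Cohort B: "If the 2 or more subjects are in Cohort B, the study will be stopped, and 1 mg/day will be declared the MTD".
- Cohort C: stop, with 2 mg as the MTD.
- Cohort D: "If the 2 or more subjects are in Cohort D, the study will be stopped, and 5 mg/day will be declared the MTD".

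**Cross-reference.** Section 2 says "Dose escalation criteria and actions, as well as subject and cohort stopping rules are detailed in" Section 6. It does not mention 15.4.

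**The concern.** Both sections are written as instructions, both end in a named dose, and they use different triggers. A cohort can satisfy the 15.4 trigger through neurologic events while having no event that 6.1 counts. Followed literally, the two sections then give different answers from the same data.

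The MTD is one of the two aims in the Study Summary. Section 2 names extrapyramidal effects as the expected dose-limiting toxicity, although for long-term use at 10 to 50 mg. The events on which the sections differ are therefore the ones the drug is known for.

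Two things are at stake: the reported MTD, and whether the next cohort is dosed. Affected subjects would not themselves move to a higher dose, because exclusion 10 in Section 7.2 bars a history of extrapyramidal signs. The exposure would fall on other subjects entering the next cohort.

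**Working it through.** **The plan's own figure.** Section 14.1 gives 3 to 24 subjects. One cohort of 3 stopped in Cohort A gives 3, and 4 cohorts × 6 = 24. Both reproduce, and neither depends on this point.

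**The rules side by side.** Take two subjects in one cohort with extrapyramidal symptoms below Grade 3.

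| Cohort and other events | Section 6.1 | Section 15.4 Scenario 2 |
|---|---|---|
| B, 6 subjects, one Grade 3 event | start Cohort C | stop, MTD 1 mg (rule c) |
| C, 3 subjects, no Grade 3 event | start Cohort D | stop, MTD 2 mg (rule d) |
| D, 3 subjects, no Grade 3 event | stop, MTD 10 mg | stop, MTD 5 mg (rule e) |

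In Cohort D the declared doses differ by a factor of 10/5 = 2. The Cohort A rules, the rule for the first three subjects of Cohort B, and Figure 1 are missing from the available text and are not judged.

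**Is the neurologic trigger ungraded?** The Grade 3 condition could grammatically be stretched over the whole Scenario 2 list. Two things speak against that. The list includes vermicular tongue movements, which Section 10 describes as a possible early sign at which stopping may prevent the full syndrome; waiting for Grade 3 would defeat that purpose. And a related Grade 3 event recurring in two subjects is already covered by the last part of the trigger, so naming the syndromes would add little.

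**How often would it happen?** The documents give no rate. Let q be the assumed chance that a subject has such symptoms below Grade 3, with subjects independent.

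1. Cohort of three, no Grade 3 event: P(at least 2 of 3) = 3q²(1−q) + q³.
   - q = 0.02: 0.001176 + 0.000008 = 0.0012
   - q = 0.05: 0.007125 + 0.000125 = 0.0073
   - q = 0.10: 0.027 + 0.001 = 0.0280
2. Cohort C or Cohort D, if both are run at the same q: 1 − (1−p)², where p is the result of step 1. This gives 0.0024, 0.0144 and 0.0552.
3. Cohort expanded to 6 with exactly one Grade 3 event: P(at least 2 of the other 5) = 1 − (1−q)⁵ − 5q(1−q)⁴. This gives 0.0038, 0.0226 and 0.0815. These figures are conditional on the expansion having occurred.

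**Cohort D with expansion allowed for.** Let r be the chance of a Grade 3 or higher event, assumed to be 10%.

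- 6.1 declares 10 mg with probability (1−r)³ + 3r(1−r)²(1−r)³ = 0.729 + 0.243 × 0.729 = 0.906.
- The part of this in which 15.4 declares 5 mg is 3q²(1−r−q) + q³ + 3r[(1−r)⁵ − (1−r−q)⁵ − 5q(1−r−q)⁴].
- At q = 0.05: 0.0065 + 0.0049 = 0.0114. At q = 0.10: 0.0250 + 0.0174 = 0.0424.

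**The case against.** The strongest reply is that the rules run in sequence. Section 15.4 acts at once, while the interim analysis in Section 3.5.1 waits until all three subjects have completed 21 days. If 15.4 has already stopped the study, the lines in 6.1 that open the next cohort are never reached. As a reading of intent for Cohorts B and C this is very probably right. It does not settle Cohort D, where both sections stop the study and name different doses, and no available sentence says that the 15.4 dose is the one to report.

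A second reply is that the extract of 6.1 is incomplete. Section 2 says that Section 6 holds subject and cohort stopping rules, so a definition of toxicity or a link to 15.4 may stand in the lost part. This stands as a limit: the point concerns the available text only.

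A reader might also infer three stronger things that the documents do not support.

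- *That the close of 15.4 confines the stop to Cohort A.* Its last sentence ends with "Grade 3 felt to be causally related to TFP at the lowest dose level", but it restates rule b and does not cancel rules c to e.
- *That mild events are the expected form.* Section 10 describes restlessness that often passes by itself, but it assigns no CTCAE grades and also describes dystonia with breathing difficulty. Section 3.4 reports more akathisia on 15 mg, no difference in Parkinsonism or dystonia, and a side effect profile similar to placebo at 2 to 6 mg. Section 3.5 expects the more severe effects, extrapyramidal symptoms among them, to be less likely at 10 mg or below.
- *That subjects would in practice be dosed after a stop.* That would require the investigator to pass over an explicit stopping rule.

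**Conclusion.** The inconsistency is real in the available text: followed literally, two decision rules return different results from the same cohort. It goes beyond missing detail, because in Cohort D one section requires 10 mg and the other 5 mg, and in Cohort C one starts a cohort that the other forbids.

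Its size is modest. At assumed rates of 2%, 5% and 10%, a cohort of three with no Grade 3 event meets it with probability 0.1%, 0.7% and 2.8%. At 20% the figure would be 3 × 0.04 × 0.8 + 0.008 = 10.4%, but nothing in the documents supports so high a rate at these doses. All these figures assume independent subjects and an ungraded neurologic trigger.

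The AE summaries planned in Section 14.2 are unaffected, and Section 4 lists only the safety profile as the primary objective; the effect is on the MTD and on escalation. Because the consequence is a twofold difference in the declared dose and the remedy is nearly free, the text should be corrected.

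**What to change.** First check the complete Section 6.1 and Figure 1. If they already give precedence to 15.4, nothing more is needed. Otherwise:

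- In 6.1, make each line that starts the next cohort, and each line that declares 10 mg the MTD, conditional on Scenario 2 of 15.4 not having been met in that cohort.
- Add one sentence: *If Scenario 2 of 15.4 is met, rules b to e of 15.4 set the MTD.*
- Keep the neurologic triggers in 15.4 ungraded, as now written, unless the sponsor specifies a threshold. Whether mild restlessness should stop the study is a clinical choice.
- Leave the Grade 3 count in 6.1 and the closing paragraph of 15.4 as they are.

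The cost is a few sentences, with no added subjects, visits or cohorts. The downside is that the trial may stop at a lower dose after mild neurologic events, which 15.4 already implies.

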## 2 Brief Summary of Research

Diamond Blackfan anemia (DBA) is a rare inherited pure red cell aplasia. The two main non-stem cell transplant therapeutic options are corticosteroids and red blood cell (RBC) transfusions. About 80% of DBA patients initially respond to corticosteroids, however, half of the patients cannot continue due to side effects or loss of response. These patients are then typically dependent on RBC transfusions throughout life. Each of these treatments is fraught with many side effects and significant morbidity and mortality are potential consequences of hematopoietic stem cell transplantation (SCT). The majority of individuals with DBA have mutations in genes encoding structural proteins of the small or large ribosomal subunit leading to deficiency of the particular ribosomal protein (RP). Studies in zebrafish with RP deficiencies confirmed the association between RP defects, p53 activation and the appearance of a DBA phenotype. Using the RP deficient zebrafish embryo model, high throughput drug screens have demonstrated a strong hematologic response to several calmodulin inhibitors. One of these chemicals is trifluoperazine (TFP). TFP treatment of a mouse model of DBA also increased the red blood cell count and the hemoglobin (Hb) levels in the mice. TFP is a FDA-approved typical antipsychotic agent that has been available since 1958 with a well-known safety profile. In the United States, TFP is approved for the short-term treatment of generalized non-psychotic anxiety; treatment or prevention of nausea and vomiting of various causes; and, management of psychotic disorders.

In this study we aim to determine the safety and tolerability of TFP in adult subjects with DBA, as a prelude to a possible proof of concept (PoC) trial (as a separate study). TFP's expected dose-limiting toxicity is primarily neurologic (extrapyramidal) when used long-term at typical anti-psychotic doses (range 10-50 mg daily). Non-neurologic adverse effects in

subjects with DBA have not been investigated. We will perform a dose escalation study to define the safety and tolerability of lower doses of this agent in subjects with DBA.

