## 10 Risks to Subjects

Adverse reactions with TFP include drowsiness, dizziness, skin reactions, rash, dry mouth, insomnia, amenorrhea, fatigue, muscular weakness, anorexia, lactation, blurred vision, and neuromuscular (extrapyramidal) reactions. Details regarding extrapyramidal and other adverse reactions with TFP follow:

- **Neuromuscular (Extrapyramidal) Reactions:** These symptoms are characterized by motor restlessness. They may be of the dystonic type, or they may resemble Parkinsonism (described below).
- **Motor Restlessness:** Symptoms may include agitation or jitteriness and sometimes insomnia. These symptoms often disappear spontaneously.
- **Dystonia (Class Effect):** Symptoms of dystonia, prolonged abnormal contractions of muscle groups, may occur in susceptible individuals during the first few days of treatment. Dystonic symptoms include spasm of the neck muscles, sometimes progressing to tightness of the throat, swallowing difficulty, difficulty breathing, and/or protrusion of the tongue. While these symptoms can occur at low doses, they occur more frequently at higher doses of first generation antipsychotic drugs.
- **Pseudoparkinsonism:** Symptoms may include mask-like facies, drooling, tremors, pill-rolling motion, cogwheel rigidity, and shuffling gait.
- **Tardive Dyskinesia:** Tardive dyskinesia is a rare syndrome characterized by rhythmical involuntary movements of the tongue, face, mouth, or jaw (e.g., protrusion of tongue, puffing of cheeks, puckering of mouth, chewing movements). These symptoms may be accompanied by involuntary movements of extremities. In rare instances, these involuntary movements of the extremities are the only manifestations of tardive dyskinesia. Symptoms may persist for months or years and, while they gradually disappear in some subjects, they may be irreversible in others. The risk appears to be greatest in elderly subjects (especially women) on prolonged, high-dose therapy. There is no known effective treatment for tardive dyskinesia. It has been reported that fine vermicular movements of the tongue may be an early sign of the syndrome and if the medication is stopped at that time the syndrome may not develop.
- **Adverse Reactions Reported with TFP or Other Phenothiazine Derivatives:** Adverse effects with different phenothiazines vary in type, frequency, and mechanism of

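### In the visible 3+3 rules a single TFP-related neurologic stop below Grade 3 reads as 0/3, so the cohort escalates or 10 mg/day becomes the MTD without expansion to six

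*Combined protocol and SAP*

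**What the plan says.** Section 6.1 (General Design) sets the cohort rules. Cohort C: if there is no toxicity at or above "Grade 3 at the end of the 21 days, Cohort D will start". Cohort D: if 0/3 have toxicity at or above "Grade 3, the study will be stopped, and 10 mg/day will be declared the MTD". In both cohorts three more subjects are added only after 1/3 with toxicity of Grade 3 or higher, and two or more of six fails the dose. Cohort B's six-subject rules have the same form. Figure 1, the Cohort A rules and Cohort B's opening rule are not in the available text.

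Section 15.4 (Stopping Rules) adds a second list: extrapyramidal symptoms, signs suggestive of tardive dyskinesia, and neuroleptic malignant syndrome (NMS). The Grade 3 threshold is attached to treatment-emergent AEs, and no grade is stated for these three. For one subject (Scenario 1) the rule is: "Treatment will be immediately stopped in that subject and the subject will be discontinued from the study". For more than one subject (Scenario 2) the dose fails; for the top dose, "If the 2 or more subjects are in Cohort D, the study will be stopped, and 5 mg/day will be declared the MTD".

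Section 2 says TFP's "expected dose-limiting toxicity is primarily neurologic (extrapyramidal) when used long-term at typical anti-psychotic doses (range 10-50 mg daily"). Section 10 says dystonia "may occur in susceptible individuals during the first few days of treatment", and adds: "While these symptoms can occur at low doses, they occur more frequently at higher doses of first generation antipsychotic drugs".

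**The concern.** In a 3+3 design, expansion to six is how one worrying event among three is checked before the dose is passed. Section 15.4 already holds that two neurologic events in a cohort make the dose too high. Section 6.1 has no step that leads there from one event. If one of the first three subjects is taken off TFP for a related extrapyramidal reaction below Grade 3, the tally still reads 0/3. Cohort C then escalates to 10 mg/day, or Cohort D closes with 10 mg/day as the MTD. The two-subject rule has then been applied to three subjects, one of whom had to stop.

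Section 2 promises specific monitoring for this class of event, and the trial is meant to support a later proof-of-concept study, so the declared MTD carries forward.

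**Working it through.** Shorthand: G3+ is toxicity of Grade 3 or higher. A neurologic stop is a TFP-related extrapyramidal, tardive dyskinesia or NMS event below Grade 3.

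**The plan's own figure.** Section 14.1 gives 3 to 24 subjects. Stopping after the first three of Cohort A gives 3, and four cohorts of six give 24. Both reproduce.

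**Tracing the rules (Cohort D, first three subjects).**

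| G3+ | Neurologic stops | Section 6.1 | Section 15.4 | Outcome |
|---|---|---|---|---|
| 0 | 0 | 0/3 | none | 10 mg/day declared on three |
| 1 | 0 | 1/3 | subject stopped if related | expand to six |
| 0 | 1 | 0/3 | subject stopped | 10 mg/day declared on three |
| 0 | 2 or 3 | 0/3 | Scenario 2 | 5 mg/day declared |
| 1 | 1, another subject | 1/3 | depends on reading | expand or fail |

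The third row is the gap. It needs no assumed rate. Cohort C behaves the same way, with escalation in place of declaration.

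**Size.** All rates are assumptions. Let p be the G3+ rate and q the neurologic-stop rate, independent, per subject within 21 days. Two or three G3+ events in the first three are taken as failing. Scenario 2 is applied as two or more neurologic stops, so a mixed pair (one of each, in different subjects) does not fail. Write, for three subjects,

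A0 = (1−p)³, A1 = 3p(1−p)², B0 = (1−q)³, B1 = 3q(1−q)².

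- Single unexpanded case: A0·B1
- Expansion as written: A1(B0+B1). With the change: A1(B0+B1) + A0·B1
- Dose clears as written: A0(B0+B1) + A1·A0·[B0(B0+B1) + B1·B0]
- Dose clears with the change: the same, less A0·B1·[1 − (A0+A1)B0]
- Extra subjects per cohort: 3·A0·B1

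Worked line, p = q = 0.05: A0 = B0 = 0.8574 and A1 = B1 = 0.1354.
- Single case: 0.8574 × 0.1354 = 0.116.
- Clears as written: 0.851 + 0.116 × 0.967 = 0.963.
- Reduction: 0.116 × (1 − 0.851) = 0.017, giving 0.946.
- Extra subjects: 3 × 0.116 = 0.35.

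| p = 0.05 | q = 0.02 | q = 0.05 | q = 0.10 |
|---|---|---|---|
| Single unexpanded case | 0.049 | 0.116 | 0.208 |
| Expansion, as written | 0.135 | 0.134 | 0.132 |
| Expansion, with change | 0.185 | 0.250 | 0.340 |
| Extra subjects per cohort | 0.15 | 0.35 | 0.62 |
| Dose clears, as written | 0.972 | 0.963 | 0.936 |
| Dose clears, with change | 0.969 | 0.946 | 0.879 |
| All four clear, same rates at every dose, as written | 0.89 | 0.86 | 0.77 |
| All four clear, with change | 0.88 | 0.80 | 0.60 |

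The four-dose rows are the fourth powers of the rows above them. The reduction in one cohort is 0.003, 0.018 or 0.062 at p = 0.02, and 0.004, 0.016 or 0.052 at p = 0.10.

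**Other reading of Scenario 2.** Mixed pairs clear with probability 0.0105, 0.0225 or 0.034 as written (p = 0.05). If Scenario 2 already fails them, the as-written figures become 0.972 − 0.0105 = 0.961, 0.963 − 0.0225 = 0.941 and 0.936 − 0.034 = 0.902. With expansion, and t = 1 − (1−p)(1−q), they become (1−t)³ + 3t(1−t)⁵ = 0.952, 0.910 and 0.824.

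**The case against.** Two thresholds can coexist. Stopping one subject early is a precaution: Section 10 notes that stopping at the first tongue movements may prevent the syndrome, and that motor restlessness often settles by itself. Section 15.4 sets its own cohort threshold, more than one subject, and that may be deliberate. Section 2 expects this toxicity mainly with long-term use at higher doses. Section 3.4 reports no difference from placebo in Parkinsonism or dystonia at 15 mg/day, though more akathisia. An interim safety and tolerability analysis precedes escalation, and a medical monitor reviews cumulative AEs. The plan states no target toxicity rate, so a lower chance of clearing is not in itself better.

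Much of this stands. It shows that one neurologic stop should not fail a dose. It does not show that one should go unexamined when the plan's own failure rule needs only one more. Section 3.5.1 refers the interim analysis back to Section 6, where no visible rule acts on such a case, and Section 15.6 gives the monitor no expansion rule.

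A reader might infer more than the documents support:
- *A mixed pair escapes both rules.* The Scenario 2 wording, "neuroleptic malignant syndrome or the same SAE or treatment-emergent AE", is ambiguous. The requirement of sameness may govern only the SAE and AE items, or the whole list may be read as alternatives.
- *The stopped subject would be replaced and drop out of the tally.* Section 3.5.1 waits for three subjects to complete 21 days, but no replacement rule is visible, and Section 14.2 keeps every dosed subject in the safety analysis.
- *The plan already treats a single case as dose-limiting.* It does so for two.
- *The gap is why an MTD can rest on three subjects.* That is the written rule for any 0/3 in Cohort D.

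**Conclusion.** The gap is real in the visible rules for Cohorts C and D: one related neurologic stop below Grade 3 leads to escalation or to an MTD of 10 mg/day without expansion. Wording in the missing figure or in the Cohort A and B text could change this, though the Cohort C and D rules are explicit.

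Its size depends wholly on the assumed rates. At a 2% stop rate the change hardly alters whether a dose clears; at 10% it matters. Low rates are plausible in 21 days at up to 10 mg/day, but Section 10 does not allow them to be taken as zero. This is a cheap improvement to the decision rule rather than a flaw that undermines the trial.

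**What to change.** Add one sentence to 6.1, for every cohort: if one of the first three subjects has TFP-related extrapyramidal symptoms, signs of tardive dyskinesia or NMS of any grade within 21 days of starting, enrol three more, as after 1/3 with Grade 3 or higher toxicity. Keep the stopped subject in the denominator. Apply the existing failure rules to the six: two or more with Grade 3 or higher toxicity, or 15.4 Scenario 2. The rule for stopping an individual does not change.

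Do not extend the trigger to SAEs below Grade 3. Scenario 1 includes them, but they are a different question and are not costed here. Separately, state in 15.4 whether a mixed pair fails the dose. That choice is the sponsor's: failing it, together with the expansion, would put the chance of clearing all four doses at 0.82, 0.69 or 0.46 under the same assumptions (fourth powers of 0.952, 0.910 and 0.824).

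The cost is the extra subjects and the somewhat earlier end to escalation shown in the table. No new data are needed: 15.2 requires a relatedness judgement for each event, and 7.6.1 a documented reason for withdrawal. Four cohorts of six still cap enrolment at 24.
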